5.1.1.1 Clinical Pharmacology

5-Azacitidine is a pyrimidine nucleoside analog of cytidine. It is believed to exert its antineoplastic effects by causing hypomethylation of DNA and direct cytotoxicity on abnormal hematopoietic cells in the bone marrow. The concentration of 5-azacitidine required for maximum inhibition of DNA methylation *in vitro* does not cause major suppression of DNA synthesis. Hypomethylation may restore normal function to genes that are critical for differentiation and proliferation. The cytotoxic effects of 5-azacitidine cause the death of rapidly dividing cells, including cancer cells that are no longer responsive to normal growth control mechanisms. Non-proliferating cells are relatively insensitive to 5-azacitidine.

5.1.1.2 Pharmacokinetics

The pharmacokinetics of 5-azacitidine were studied in 6 MDS patients following a single 75 mg/m² subcutaneous (SC) dose and a single 75 mg/m² intravenous (IV) dose. 5-Azacitidine is rapidly absorbed after SC administration; the peak plasma 5-azacitidine concentration of 750 \pm 403 ng/ml occurred in 0.5 hour. The bioavailability of SC 5-azacitidine relative to IV 5azacitidine is approximately 89%, based on area under the curve. Mean volume of distribution following IV dosing is 76 \pm 26 L. Mean apparent SC clearance is 167 \pm 49 L/hour and mean half-life after SC administration is 41 \pm 8 minutes.

Published studies indicate that urinary excretion is the primary route of elimination of 5azacitidine and its metabolites. Following IV administration of radioactive 5-azacitidine to 5 cancer patients,

the cumulative urinary excretion was 85% of the radioactive dose. Fecal excretion accounted for <1% of administered radioactivity over 3 days. Mean excretion of radioactivity in urine following SC administration of 14C-5-azacitidine was 50%. The mean elimination half-lives of total radioactivity (5-azacitidine and its metabolites) were similar after IV and SC administrations, about 4 hours.

The pharmacokinetics of CC-486 as a single agent were evaluated in the phase I/II trial in MDS, CMML and AML patients. Plasma and urine studies were done on days 1 and 7 of cycle 1 (SQ dosing) and cycle 2 (oral dosing). Rapid absorption was seen in both routes as the maximum observed plasma concentration (C_{max}) was reached within 0.5 hours with SQ dosing and 1.0 hours with oral dosing. The mean elimination half-life was 1.6 ± 0.7 hours for SC and 0.62 ± 0.25 hours for oral and the concentration decreased in a pseudobiphasic manner. The MTD had a mean relative bioavailability of $13\% \pm 9\%$. Apparent volume of distribution was greater than total body water and apparent total clearance was greater than hepatic blood flow, suggestive wide tissue distribution and extrahepatic metabolism, respectively. Less than 2% of azacitidine was recovered in urine in both SQ and oral forms, implying the main elimination pathway is not renal. Tests after multiple doses suggest no azacitidine accumulation³¹.

5.1.1.3 Handling, Storage, and Disposal of CC-486

CC-486 is a cytotoxic drug and, as with other potentially toxic compounds, caution should be exercised when handling CC-486 tablets. Procedures for proper handling and disposal of anticancer drugs should be applied.

If CC-486 comes into contact with the skin, immediately and thoroughly wash with soap and water. If it comes into contact with mucous membranes, flush thoroughly with water.

CC-486 will be supplied as 100 mg tablets. Each tablet is formulated using excipients that are generally regarded as safe and are used in marketed drug products. Further details can be found in the CC-486 Investigator's Brochure. There is no need to protect CC-486 from exposure to light.

Each tablet will be sealed in a blister package. CC-486 tablets should be stored at 25°C (77°F), excursions permitted to 15°C to 30°C (59°F to 86°F), and free of environmental extremes. The storage area should be secure and have limited access. Shelf-life evaluations of the intact blister packages, pouches, and HDPE bottles are ongoing. The CC-486 study drug will be monitored for stability for the duration of the study.

5.2 Screening and Eligibility

The Investigator is responsible for keeping a record of all subjects who sign an Informed Consent Form for entry into the study. All subjects will be screened for eligibility. Screening procedures are outlined in Section 2, Schedule of Study Assessments and unless otherwise specified, must take place within 28 days prior to initiation of therapy.

5.2.1 Inclusion Criteria

Subjects must meet the following inclusion criteria to be eligible for the study:

- 1. Understand and voluntarily sign an informed consent form.
- **2.** Age ≥ 18 years at the time of signing the informed consent form.
- 3. Able to adhere to the study visit schedule and other protocol requirements.
- **4.** Subjects must have a histologically confirmed pancreatic adenocarcinoma that has had an R0 (negative margins) or R1 (microscopically positive margins) resection.
- 5. Subjects must have finished adjuvant therapy, which can include chemotherapy and/or chemoradiation therapy or have been determined to be unable to take adjuvant therapy. Although patients will be expected to complete chemoradiation or chemotherapy per physician recommendations, patients who are unable to complete chemotherapy \pm radiation therapy secondary to dose limiting toxicities will be eligible provided they meet study criteria.
- 6. Subjects enrolled due to node + disease or R1 resection must be able to undergo randomization within 3 months of finishing adjuvant therapy or the decision that they are unable to take adjuvant therapy. Patients enrolling due to CA 19-9 elevations can enroll any time after adjuvant therapy has completed.
- 7. All previous cancer therapy including radiation, chemotherapy, and surgery, must have been discontinued at least 4 weeks prior to treatment in this study
- 8. Subjects must either have a CA 19-9 value > the institutional ULN on two separate checks at least 2 weeks apart OR have had an R1 resection margin OR N1 nodal disease regardless of CA 19-9 level
- **9.** Subjects must be free of visible disease on imaging (CT, PETCT or MRI) evaluating chest, abdomen, and pelvis within 28 days of enrollment on the study.
- 10. Life expectancy of greater than 12 weeks
- **11.** ECOG performance status of ≥ 1 at study entry (see Appendix A).
- **12.** Subjects must have normal organ and marrow function as defined below:

- Absolute neutrophil count $\geq 1500/\text{mm}^3$
- Leukocytes \geq 3,000/mm³
- Platelet count \geq 100,000/mm³
- Hemoglobin > 9.0 g/dL
- Serum creatinine levels $\leq 2 \text{ mg/dL}$
- Serum bilirubin levels $\leq 1.5 \text{ mg/dL}$
- AST (SGOT) and ALT (SGPT) \leq 2.5 x ULN
- Alkaline phosphatase $\leq 2.5 \text{ x ULN}$
- **13.** Free of prior malignancies for ≥ 5 years with exception of currently treated basal cell, squamous cell carcinoma of the skin, or carcinoma *in situ* of the cervix or breast.
- 14. Women of childbearing potential should be advised to avoid becoming pregnant and men should be advised to not father a child while receiving treatment with CC-486 or *nab*-paclitaxel. All men and women of childbearing potential must use effective methods of birth control throughout the study and for three months after completing treatment.
- 15. Women of childbearing potential must have a negative serum or urine β -hCG pregnancy test at screening.
- **16.** Subjects must have < Grade 2 pre-existing peripheral neuropathy (per CTCAE)

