5.2.2 Exclusion criteria

Subjects who meet any of the following exclusion criteria are not eligible for the study:

- 1. Any serious medical condition, laboratory abnormality, or psychiatric illness that would prevent the subject from signing the informed consent form.
- 2. Pregnant or breastfeeding women.
- 3. Use of any other chemotherapy, radiotherapy, or experimental drug or therapy within 4 weeks (6 weeks for nitrosoureas or mitomycin C) prior to enrollment on study or those who have not recovered from adverse events ≥ grade 1 due to agents administered more than 4 weeks earlier except for stable grade 2 neuropathy.
- 4. Subjects may not receive any other concomitant investigational agents.
- 5. Known or suspected hypersensitivity to 5-azacitidine or mannitol

- **6.** Known positive for HIV or infectious hepatitis, type B or C. HIV patients are at increased risk of lethal infections when treated with marrow-suppressive therapy.
- 7. Uncontrolled intercurrent illness including, but not limited to, ongoing or active infection, symptomatic congestive heart failure, unstable angina pectoris, cardiac arrhythmia, or psychiatric illness/social situations that would limit compliance with study requirements.
- 8. Any known gastrointestinal disorders which would preclude oral administration of 5azacitidine.

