5.3.2.2 Arm A for first 12 cycles

Arm A patients will be evaluated on Day 1 of every cycle with a physical examination, ECOG performance status, vital signs, weight, CBC with differential, research blood and serum chemistry and hepatic panel. Arm A patients will also complete an assessment of adverse events and reporting of current medications/procedures on Day 1 of every cycle.

Arm A patients will complete a CA 19-9, quality of life assessment and CT scan on Day 1 of every third cycle beginning at Cycle 4.

Arm A subjects will be evaluated for adverse events on Day 1 of each cycle with the NCI CTCAE v4.0 (http://ctep.info.nih.gov) used as a guide for the grading of severity. For Arm A patients, doses will be reduced for hematologic and other non-hematologic toxicities that can be attributed to the study drug. Dose adjustments are to be made according to the system showing the greatest degree of toxicity. When a dose reduction is required for Day 1 of any cycle, no dose re-escalation will be permitted for the duration of study treatment.

NOTE: Arm B patients will not be evaluated for adverse events as they do not receive the study agent.

Criteria to Initiate Treatment

In Arm A, a new course of treatment may begin on the scheduled Day 1 of a new cycle if:

- Absolute neutrophil count $\geq 1500/\text{mm}^3$
- Platelet count $\geq 100,000/\text{mm}^3$
- Serum creatinine levels < 2 mg/dL
- Serum bilirubin levels $\leq 1.5 \text{ mg/dL}$.
- AST (SGOT) and ALT (SGPT) \leq 2.5 x the institutional upper limit (ULN) of the normal range
- Any other drug-related adverse events that may have occurred must have resolved to < Grade 2 severity except grade 2 anorexia and any correctable metabolic abnormality.
- No evidence of visible disease recurrence on imaging (if indicated per Study Schedule, Section 2, to be done prior to cycles 4, 7, and 10)

If these conditions are not met on Day 1 of a new cycle, the subject will be evaluated weekly and a new cycle of treatment will not be initiated until the toxicity has resolved as described above utilizing the dose modifications as depicted below. If the study drug has to be held for > 28 days, study treatment will be discontinued.

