5.4 Discontinuation of Treatment: Arm A

In the absence of treatment delays due to adverse events, treatment with CC-486 may continue until one of the following criteria applies:

• Interruption of scheduled therapy for greater than four weeks,

- Intercurrent illness that prevents further administration of treatment,
- Adverse event(s) that, in the judgment of the Investigator, may cause severe or permanent harm or which rule out continuation of the treatment regimen
- For any grade 3 and 4 toxicity that recurs despite dose reduction
- Discontinuation of CC-486 for any reason,
- Treatment with other chemotherapeutic or investigational anti-neoplastic drugs,
- Subject decides to withdraw from the study,
- Suspected pregnancy or positive pregnancy, or
- General or specific changes in the subject's condition render the subject unacceptable for further treatment in the judgment of the investigator, or
- Disease recurrence on imaging, or
- Patient has completed one year of therapy with CC-486.

If the subject has visible disease recurrence on imaging or meets any of the aforementioned criteria for removal from study treatment, then the CC-486 or observation phase of this study will conclude and patient will enter the follow-up phase of the study, following the schedule of assessments as described in Section 5.4.2.9.

Mandatory research bloods and tumor biopsies will be obtained at the time of recurrence for both Arm A and Arm B subjects, per the method determined best per the investigator as outlined on the Study Calendar and in Section.

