Appendix A: ECOG Performance Status Scale

SCORE	DESCRIPTION
0	Fully active, able to carry on all pre-disease performance without restriction.
1	Restricted in physically strenuous activity but ambulatory and able to carry out work of a light or sedentary nature, e.g., light house work, office work.
2	Ambulatory and capable of all self-care but unable to carry out any work activities. Up and about more than 50% of waking hours.
3	Capable of only limited self-care, confined to bed or chair more than 50% of waking hours.
4	Completely disabled. Cannot carry on any self-care. Totally confined to bed or chair.
5	Dead.

-

INSTRUCTIONS:

1. Complete one form per cycle of therapy.

- 2. Take your dose of the study drug days 1 through 21 of each 28 day cycle. CC-486 may be taken on an empty stomach or with food. The tablets should be taken with about 1 cup (240mL) of water. You will take 3 tablets each day (or fewer if you have been dose reduced by your physician). You should swallow the tablets whole. Do not chew, crush, or break the tablets. If a dose of CC-486 is missed, it should be taken as soon as possible on the same day. If it is missed for the entire day, it should not be made up. If the patient vomits after a dose is taken, no more subsequent tablets should be administered.
- 3. Record the date, the number of tablets of you took, and when you took them.
- 4. If you have any comments or notice any side effects, please record them in the Comments section.
- 5. Please return the forms to your physician/research nurse prior to the next cycle of therapy.
- 6. On clinic days-please wait to take your medication until after you have been seen by the RN or Doctor

[figure not shown]
Day	Date	What time was the dose taken?	Comments
1			
2			
3			
4			
5			
6			
7			
8			
9			
10			
11			

12						
13						
14						
15						
16						
17						
18						
19						
20						
21						
To be completed by research study staff:						
1. Date protocol treatment was started						
2. Date subject was removed from protocol						
3. Planned total daily dose						
4. Total number of pills taken this cycle						
5. Research Study Staff's Signature:						

Participant's signature	Date	

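### Inclusion criterion 11 requires ECOG ≥ 1, which as written excludes fully active patients and sets no upper limit on poor performance status

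*Combined protocol and SAP*

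**What the plan says.** Section 5.2.1 lists criteria that every subject has to meet. Item 11 is "ECOG performance status of ≥ 1 at study entry (see Appendix A"). Appendix A describes grade 0 as "Fully active, able to carry on all pre-disease performance without restriction" and grade 4 as "Completely disabled. Cannot carry on any self-care. Totally confined to bed or chair", so a higher score means worse function.

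ECOG is recorded at screening and on Day 1 of each Arm A cycle (sections 2.1, 5.3.1 and 5.3.2.2). The schedule footnote and the screening text refer to Appendix A for the scale but give no threshold.

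Other entry rules bear on frailty indirectly: item 3 ("Able to adhere to the study visit schedule and other protocol requirements"), item 10 (life expectancy above 12 weeks), item 12 (organ and marrow function) and exclusion 7 ("Uncontrolled intercurrent illness including, but not limited to, ongoing or active infection"). Dosing is outpatient (section 5.2.9).

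**The concern.** A lower bound on a scale where 0 is best works in the opposite direction from a fitness requirement: it turns away the fittest patients and leaves the least fit unbounded. Two things are at stake.

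- **Who is eligible.** Every ECOG 0 patient enrolled would fail a mandatory criterion. Section 5.2.6 tells sites to follow the protocol as written, section 5.2.7 has the Coordinating Center confirm eligibility, and section 10.3 has the Protocol Chair monitor it. Four institutions take part (section 5.1). If some apply the text literally and others what they take it to mean, they will enrol different populations under one protocol.
- **Patient protection.** There is no numeric performance-status safeguard at entry. Section 5.1.1.3 states that "CC-486 is a cytotoxic drug and, as with other potentially toxic compounds", it needs careful handling, and section 3.3.2 lists its adverse reactions. Item 5 admits patients judged unable to take adjuvant therapy, so reduced performance status is plausible in this population.

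**Working it through.** No formula applies. The check applies item 11 to each living grade in Appendix A and then looks for any other text that would repair it.

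**Step 1: apply the criterion.** The last column reverses the sign for comparison only.

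| ECOG grade (Appendix A, summarised) | Item 11 as written (≥ 1) | Sign reversed (≤ 1) | Readings agree? |
|---|---|---|---|
| 0, unrestricted | fails | meets | no |
| 1, limited in strenuous activity | meets | meets | yes |
| 2, self-caring but not working | meets | fails | no |
| 3, limited self-care | meets | fails | no |
| 4, totally disabled | meets | fails | no |

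As written, the eligible set is {1, 2, 3, 4}, or 4 of 5 grades. Reversed, it is {0, 1}, or 2 of 5. The readings differ on {0, 2, 3, 4}, or 4 of 5, and agree only on grade 1.

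**Step 2: look for another ECOG entry limit.** There is none in the synopsis, section 2 and its footnotes, section 5.1, the rest of 5.2.1, the exclusions in 5.2.2, or the screening text in 5.3.1. The schema figure is missing from the copy reviewed and could not be checked. The wording of the eligibility checklist is not in the documents.

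**Step 3: look for a later ECOG gate in Arm A.**

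- Section 5.3.2.2 says "a new course of treatment may begin on the scheduled Day 1 of a new cycle if" certain conditions hold: neutrophils, platelets, creatinine, bilirubin, AST/ALT, other drug-related adverse events, and no visible recurrence. That is 7 conditions, of which 0 use ECOG.
- Section 5.4 has 11 discontinuation bullets, of which 0 use an ECOG value. The nearest covers changes that "render the subject unacceptable for further treatment in the judgment of the investigator", which is a matter of judgement.
- Section 7.3.6.2 gives a fall of more than one ECOG level as an example of symptomatic deterioration to be reported as progression. It is a relative change, placed under the follow-up-phase rules, and sets no entry limit. It does confirm that higher scores are worse.

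**Step 4: could the symbol be a text-extraction error?** The same list shows ≥ used sensibly for age (item 2) and years free of prior malignancy (item 13), and ≤ for creatinine and bilirubin (item 12). Both symbols therefore survived extraction nearby. An isolated error in item 11 is unlikely but cannot be ruled out without the source file.

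**The case against.** The best case for leaving this alone is that it is an obvious slip that experienced sites will read correctly. The randomised comparison is untouched, no sample size, power or alpha figure changes, and the number of patients affected is unknown. Item 3, item 10, item 12, exclusion 7 and outpatient dosing already make ECOG 4 entry unlikely. Section 3.4 describes azacitidine as very well tolerated, and section 11.3.5 provides a stopping guideline for grade 3/4 toxicity. Only Arm A is exposed to the drug, and the absence of ECOG values from later treatment rules is partly a matter of preference, since section 5.4 leaves room for investigator judgement.

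Much of this is fair. There is no bias between arms, the indirect rules do screen out some frail patients, and the counts from sections 5.3.2.2 and 5.4 show only that nothing downstream replaces the entry limit; they are not defects in themselves. None of it repairs item 11. The indirect rules set no performance-status limit and cannot make an ECOG 0 patient eligible. The toxicity guideline acts after exposure, not at entry. Central review would be checking patients against the same faulty text unless the checklist differs. That sites may guess the intended meaning is a reason to correct the wording.

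**Conclusion.** The concern holds. Item 11 as written excludes ECOG 0 and gives no upper bound, and nothing else in the readable documents corrects either fault. The literal and sign-reversed readings disagree on 4 of the 5 living grades. These are counts of scale categories, not patients; the share of patients affected cannot be estimated from the documents. ECOG 2 and some ECOG 3 patients could enter under the literal text; ECOG 4 entry is unlikely because of the other rules.

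The consequence is a misdefined eligible population, a missing safeguard at entry and uncertainty about whom the results describe, with no effect on the validity of the between-arm comparison. Because this is a wrong threshold in a binding eligibility rule, it must be fixed. The conclusion assumes that the symbol in the source file matches the text reviewed and that the missing schema figure carries no ECOG limit.

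**What to change.** Check the symbol in item 11 against the source file. If it stands, amend item 11 so that, read with Appendix A, it states the sponsor's intended upper limit on ECOG and leaves no doubt whether grade 0 is eligible. The documents do not give the limit, so the sponsor must supply it. Confirm that the eligibility screening checklist named in section 5.2.7 carries the same wording at all four institutions.

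A separate, minor point that does not affect the weight given above: inclusion 16 requires peripheral neuropathy below grade 2, while exclusion 3 makes an exception for stable grade 2 neuropathy. For peripheral neuropathy that exception admits nobody, so the two items should be reconciled.

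The cost is a short text amendment and a checklist check. The amendment needs company review and IRB/EC approval (sections 9.1 and 12.1). No design or analysis figure changes.

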5.2.2 Exclusion criteria

Subjects who meet any of the following exclusion criteria are not eligible for the study:

- 1. Any serious medical condition, laboratory abnormality, or psychiatric illness that would prevent the subject from signing the informed consent form.
- 2. Pregnant or breastfeeding women.
- 3. Use of any other chemotherapy, radiotherapy, or experimental drug or therapy within 4 weeks (6 weeks for nitrosoureas or mitomycin C) prior to enrollment on study or those who have not recovered from adverse events ≥ grade 1 due to agents administered more than 4 weeks earlier except for stable grade 2 neuropathy.
- 4. Subjects may not receive any other concomitant investigational agents.
- 5. Known or suspected hypersensitivity to 5-azacitidine or mannitol

- **6.** Known positive for HIV or infectious hepatitis, type B or C. HIV patients are at increased risk of lethal infections when treated with marrow-suppressive therapy.
- 7. Uncontrolled intercurrent illness including, but not limited to, ongoing or active infection, symptomatic congestive heart failure, unstable angina pectoris, cardiac arrhythmia, or psychiatric illness/social situations that would limit compliance with study requirements.
- 8. Any known gastrointestinal disorders which would preclude oral administration of 5azacitidine.

